**Safety and Efficacy of Donepezil in Mild to
Moderate Alzheimer's Disease: A Multi-center
Single-arm Study in China**

Protocol & SAP Synopsis

2016.10.09

NCT02787746

PROTOCOL TITLE	Safety and Efficacy of Donepezil in Mild to Moderate Alzheimer's Disease: A Multi-center Single-arm Study in China
STUDY SPONSOR	Beijing Friendship Hospital & Eisai (China) Pharmaceutical Co., Ltd.
STUDY PHASE	4
INDICATION	For the treatment of mild to moderate Alzheimer's disease.
PRIMARY ENDPOINT	Monitoring and recording the count and incidence of adverse events (AEs).
SECONDARY ENDPOINTS	
 • Monitor and record the number of patients withdrew from trial for adverse events. • Change from baseline to 20 weeks in MMSE scores. • Change from baseline to 20 weeks in ADL scores. • Correlation analysis between Apo-E genotyping and adverse events of donepezil.
STUDY DESIGN	This is a Phase 4 multi-center, single-arm, open labeling study.
SAMPLE SIZE	The main indicator of this study was the incidence of adverse events in the treatment of Alzheimer's disease with 10 mg donepezil hydrochloride tablets. According to the safety data in the comprehensive literature, the incidence of adverse events is basically between 69.4%-81%, and the expected total incidence of adverse events is about 76%, estimated with a 95% confidence interval. With reference to the research data, the width of the confidence interval for the incidence of adverse events is 8%, and the significance level is set as 0.05. The sample size is estimated to be 461 cases by using PASS11.0 software. Considering the 20% drop out rate, 554 cases are finally planned to enter the group.

ELIGIBILITY CRITERIA	
Inclusion Criteria:
 
 1. Patients between 50 and 85 years of age. 2. Patients newly diagnosed as probable AD based on Diagnostic and Statistical Manual of Mental Disorders, 4th Edition, Text Revision (DSM-IV-TR) criteria and National Institute of Neurologic and Communicative Disorders and Stroke—AD and Related Disorders Association (NINCDS-ADRDA) criteria; Mild to moderate AD with Mini-Mental State Examination (MMSE) 10-24, modified Hachinski ischaemic scale (MHIS)≤4, Activity of daily life scale (ADL)≥23, and Hamilton Depression Scale (HAMD) <7. 3. MRI image supports the diagnosis of AD (medial temporal lobe atrophy, Fazekas scale of white matter lesions≤2 within 6 months prior to the screening). 4. 5mg daily of Donepezil for at least four weeks before the screening. 5. Patient with exclusive caregiver. 6. Patient should be ambulatory or ambulatory aided by a walker or cane. 7. With good eyesight and hearing, can cooperate with the examination and treatment. 
Exclusion Criteria:
 
 1. Patients with vascular dementia, other types of dementia or with other psychiatric or neurological disorders (e.g. delirium, depression, Parkinson's disease, etc.). 2. Patients with type I diabetes, obstructive lung disease or asthma, vitamin B₁₂ or folic acid deficiency, thyroid dysfunction, severe liver or kidney dysfunction, severe cardiac insufficiency (congestive heart failure, myocardial infarction, sick sinus syndrome, II-III degree atrioventricular block or heart rate<50 beats/minute [bpm]). 3. Epilepsy or head trauma resulting in unconsciousness that occurred in the two years prior to the screening. 4. Patients with hematologic diseases (such as anemia, granulocytes, leukemia, etc.), tumor, neoplasms within 2 years prior to the screening. 5. Patients with a history of alcohol dependence and drug abuse. 6. Patients with known hypersensitivity to medicines or
----------------------	---

	
foods;
 
 7. Patients taking anticholinergic agents or antihistaminic agents; 8. Patients who had been hospitalized continuously for more than 3 months before the screening.
DRUG DOSAGE AND FORMULATION	Once a day, two tablets at a time. Take it orally before bed at night (insomniacs can take it after breakfast). If the subject cannot tolerate 10 mg, he can return to the 5 mg dose, and after 4 weeks of use, increase the dose to 10 mg for the second time. If the second dose is increased to 10 mg and can not tolerate, the person who returns 5 mg or discontinues the drug is considered to be discontinued.
ROUTE OF ADMINISTRATION	Oral
TREATMENT DURATION	Use 10mg dose for 20 weeks.

PROCEDURES	
Subjects conducted 3 visits at baseline (-5 to 0 days), maintained 10mg dose within 7 days after 4 weeks and maintained 10mg dose for 20 weeks \pm7 days, during which the follow-ups of subjects can be increase at any time with safety of drug .
 
Visit 1 baseline (- 5 to 0 days)
 
 1. The purpose of this visit is to examine whether the subjects are suitable for the study. 2. The subjects and their guardians sign the informed consent form after understanding the research. 3. General information collection: fill in demographic data, inquire about allergy history, inquire about past diseases, record combined diseases and medication, etc. 4. Vital signs measurement. 5. MMSE score, MIS score, ADL score, HAMD score. 6. Laboratory inspection. 7. Syphilis, folic acid and vitamin B12 examination, thyroid function T3, T4 examination. 8. Head MRI (head MRI should include axial position and coronal position. Previous head MRI with diagnostic reference value can be exempted from this item, but it should have detailed image description). 9. ECG examination. 10. Record adverse events. 11. Record combined medication. 12. Inform the subjects to follow up within 7 days after maintaining the dose of 10mg for 4 weeks. If the subjects have any questions or abnormal conditions during this period, they can contact the researchers at any time.
-------------------	---

	
Visit 2 (maintain 10mg dose within 7 days after 4 weeks)
 
1. Check whether the subjects take the medicine strictly according to the clinical trial plan.2. Vital signs measurement.3. MMSE score, ADL score.4. APOE genotyping test.5. Blood biochemical examination.6. ECG examination.7. Record adverse events.8. Record combined medication.9. Instruct the subjects to follow up after being enrolled for 20 weeks. If the subjects have any questions or abnormal conditions during this period, they can contact the researchers at any time. 
Visit 3 (maintain 10 mg dose for 20 weeks ± 7 d)
 
1. Check whether the subjects take the medicine strictly according to the clinical trial plan.2. Vital signs measurement.3. MMSE score, ADL score.4. Laboratory inspection.5. ECG examination.6. Record adverse events.7. Record combined medication.
--	--

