1.8 Other Safety Data Analysis

For the QT interval and heart rate before and after treatment, the mean, median, standard deviation, maximum, minimum, 25%, 75% quantiles were used for statistical description, and the scores before and after treatment were paired t-tested. At the same time, the 95% confidence interval of the change value before and after treatment is obtained. Based on the predetermined MCID value, the 95% confidence interval is compared with the lower limit of the 95% confidence interval to determine whether the changes in QT interval and heart rate have clinical significance.

For vital signs, the mean, median, standard deviation, maximum, minimum, and 95% confidence intervals were used to describe the changes in vital signs at each follow-up point.

For laboratory examination and ECG, the clinical significance judgment and frequency (or frequency) of all indexes before and after treatment are made in a cross table, and the details of abnormal examination items after treatment are listed.

For quantitative laboratory test values, list the mean, median, standard deviation, maximum, minimum, 25%, 75% quantiles, and paired t-test for the scores before and after treatment to obtain 95% confidence interval of the changed value to evaluate its safety.

● **Adverse Events**

When filling out the adverse event form, the researcher should use mild, moderate, and severe to describe the intensity of the adverse event. To unify the standard, the classification of event intensity is as follows:

Moderate: To some extent affects the normal function of the subject.

Severe: Obviously affect the normal function of the subject.

- Mild: Does not affect the normal function of the subject.
- Moderate: To some extent affects the normal function of the subject.
- Severe: Obviously affect the normal function of the subject.

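### Visits 2 and 3 are tied to time maintained on 10 mg and no assessment is described at discontinuation, so the paired safety comparisons draw mainly on patients who tolerated 10 mg

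*Protocol*

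**What the plan says.** - **Timing of visits.** The introduction to PROCEDURES in the Protocol places the post-baseline visits at "maintained 10mg dose within 7 days after 4 weeks and maintained 10mg dose for 20 weeks". The visit headings repeat this: "Visit 2 (maintain 10mg dose within 7 days after 4 weeks" and "Visit 3 (maintain 10 mg dose for 20 weeks ± 7 d".
- **Visit 2 item 9** uses a different clock for the last visit: "Instruct the subjects to follow up after being enrolled for 20 weeks".
- **Extra visits.** The introduction allows them: "during which the follow-ups of subjects can be increase at any time with safety of drug". It lists no tests for them and does not tie them to stopping.
- **Stopping.** Under DRUG DOSAGE AND FORMULATION, a first intolerance leads to 5 mg and a second increase after 4 weeks. After a second intolerance, "the person who returns 5 mg or discontinues the drug is considered to be discontinued". No assessment is attached to that event.
- **Content of visits.** Visit 2 lists vital signs, blood biochemistry and ECG. Visit 3 lists vital signs, laboratory inspection and ECG. Section 1.5 defines the laboratory indicators as blood routine, urine routine and biochemistry.
- **Analysis.** Section 1.8 plans paired t-tests "For the QT interval and heart rate before and after treatment" and for quantitative laboratory values, with cross tables for laboratory and ECG findings. The SAP plans paired t-tests for ALT, AST, HR, QT and QTc. Neither says which visit supplies the second value.

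**The concern.** Safety is the main purpose of this single-arm study. If a reading is scheduled only once 10 mg has been maintained for a set time, a second reading is least likely in patients who could not maintain it. Some of them may have stopped because of a slow heart rate, an ECG change or raised liver enzymes. A paired test drops anyone without a second value, so the mean changes and cross tables would look more favourable than in all treated patients if leavers respond worse than stayers. LOCF does not help: section 1.3 applies it to the main variables and the SAP to efficacy, and no imputation recovers a reading that was never taken. With the *after* value undefined, an analyst could also choose Visit 2, Visit 3 or the last value once the data are known.

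**Working it through.** **1. The plan's own figures.** An exact (Clopper-Pearson) 95% interval at 76% first has full width no more than 8% at n = 461 (width 0.07996), which matches the plan. Enrolment of 554 is 461 × 1.2 = 553.2, rounded up. At the plan's 20% dropout, 554 × 0.20 = 110.8, so about 111 leave and 443 remain. The documents do not say when or why they leave.

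**2. What is scheduled after baseline, by patient path.**

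| Path | Vital signs, biochemistry, ECG | Blood and urine routine |
|---|---|---|
| Stops for good before 4 weeks on 10 mg | None | None |
| Steps down, returns to 10 mg, maintains it 4 weeks, then stops | Visit 2 | None under the Visit 3 heading |
| Stops after Visit 2 without a step-down | Visit 2 | None under the Visit 3 heading |
| Maintains 10 mg for 20 weeks | Visits 2 and 3 | Visit 3 |

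**3. The two anchors for Visit 3.** Assume 10 mg starts at enrolment. For a patient who never interrupts, the two clocks agree. For one who steps down and returns, at least 4 weeks are spent on 5 mg. Twenty weeks on 10 mg is then reached no earlier than 20 + 4 = 24 weeks after enrolment, and later if the count restarts. The gap of at least 4 weeks exceeds the 7-day window. For a patient who stops for good after Visit 2, the heading gives no Visit 3, while item 9 can be read as giving one up to about 20 − 4 = 16 weeks after stopping.

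**4. Size, as an illustration only.** If a fraction *f* has no paired value, the mean change in those with a value differs from the mean in everyone by

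bias = *f* × (mean change in stayers − mean change in leavers).

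The 95% half-width is 1.96 × SD / √n, with n = 554 × (1 − *f*). Assumptions not in the documents: SD of heart-rate change 8 bpm; leavers differ from stayers by 3, 5 or 8 bpm.

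| *f* | n | Bias at 3 bpm | Bias at 5 bpm | Bias at 8 bpm | Half-width |
|---|---|---|---|---|---|
| 5% | 526 | 0.15 | 0.25 | 0.40 | 0.68 |
| 10% | 499 | 0.30 | 0.50 | 0.80 | 0.70 |
| 20% | 443 | 0.60 | 1.00 | 1.60 | 0.74 |

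For example, 0.20 × 5 = 1.0 bpm and 1.96 × 8 / √443 = 0.74 bpm; 0.10 × 5 = 0.5 bpm and 1.96 × 8 / √499 = 0.70 bpm. The 20% row applies if all planned dropouts leave before Visit 2, or if *after* is taken to mean Visit 3 only. The 10% row would apply, for instance, if half of them leave after Visit 2 and their Visit 2 value is used.

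**The case against.** The best case for the plan has five parts.

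- **Visit 2 covers later leavers.** This stands for vital signs, biochemistry (including ALT and AST) and ECG. A reader might infer that nobody who stops 10 mg has a scheduled reading, or that the analyses describe only patients who tolerated the drug. The documents do not support either. Visit 2 readings exist, section 1.8 describes vital signs at each follow-up, and a first step-down can be followed by a return to 10 mg and attendance at both visits. What remains is the patient who stops for good before Visit 2, and blood and urine routine for those who stop after it.
- **Extra follow-ups are allowed.** True, but they are optional and carry no list of tests, so what is collected would vary by site.
- **Item 9 calls patients back at 20 weeks.** It is an instruction given at Visit 2, so it does not reach those who stop before then. For later leavers it conflicts with the Visit 3 heading and would yield a reading taken off 10 mg.
- **The primary endpoint is AE incidence, and the safety set does not require completion.** This stands. The point concerns the paired ECG and laboratory analyses, and a recorded AE counts without a second ECG. But belonging to the safety set does not supply a missing second value.
- **The Protocol is headed as a synopsis.** A fuller text may describe exit assessments. The text supplied lists each visit item by item and includes none.

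**Conclusion.** The concern holds in a limited form and is worth a short amendment. As written, the schedule loses safety readings selectively in patients who stop for good before 4 weeks on 10 mg and, under the Visit 3 heading, loses blood and urine routine in those who stop later. The paired comparisons therefore lean towards patients who tolerated 10 mg, their second value is undefined, and the timing of Visit 3 is contradictory.

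A reader might take 1.0 bpm as the size of the bias. The documents do not support that. It requires all 20% to lack a paired value, and the SD and the difference are assumed. Within the range shown, the bias runs from negligible (0.15 bpm) to about twice the half-width (1.6 against 0.74 bpm). Section 1.8 judges QT and heart rate against a predetermined MCID whose value is not given, so whether a bias of this order would change a conclusion cannot be determined. That it favours the drug also assumes that leavers respond worse than stayers.

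**What to change.** 1. **Reconcile the Visit 3 timing.** The PROCEDURES introduction and the Visit 3 heading count time on 10 mg; Visit 2 item 9 counts from enrolment. The sponsor must decide which is meant and make the passages agree, including for patients who step down and return.
2. **Collect the existing Visit 3 safety assessments when a patient is considered discontinued or leaves the study.** Record the date of the last dose and the dose taken. Dosing and stopping rules stay as they are, and no new type of test is added.
3. **Define the paired comparison in section 1.8 and the SAP.** Suggested text: *The main paired comparison for ECG and quantitative laboratory variables is baseline to the last available post-baseline value in the safety set. Values taken after stopping are flagged, and the number of patients without any post-baseline value is reported. The comparison in patients with Visit 3 data is a sensitivity analysis.*

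The cost is a short amendment and, for each leaver, one visit brought forward. Some leavers will not attend, so the gap will shrink but not close. Values taken after stopping may partly reflect recovery, which is why they need the flag and the date of last dose.

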1.4 Efficacy Endpoints

- Primary Efficacy Endpoints

Monitoring and recording the count and incidence of adverse events (AEs).

- Secondary Efficacy Endpoints

1. Monitor and record the number of patients withdrew from trial for adverse events.
2. Change from baseline to 20 weeks in MMSE scores.
3. Change from baseline to 20 weeks in ADL scores.
4. Correlation analysis between Apo-E genotyping and adverse events of donepezil.

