Safety and Efficacy of Donepezil in Mild to Moderate Alzheimer's Disease: A Multi-center

Single-arm Study in China

NCT02787746

September 18, 2016

Statistical Analysis Plan (SAP)

Safety analysis is conducted on the safety set (SS, patients who receive at least one dose of donepezil 10mg/day and have at least one safety evaluation). Efficacy analysis is conducted on the per protocol analysis set (PPS, patients who complete the study with no major protocol violations) with last observation carried forward (LOCF) as well as the full analysis set (FAS, all enrolled patients are included) LOCF. In addition, in order to test the robustness and accuracy of our results, efficacy analysis is further conducted on the PPS and FAS wherein missing data is not filled in and not included and thus only actual data of every patient who take the efficacy test are included (FAS [actual number] and PPS [actual number], respectively).

For the safety analysis, overall incidence of AEs and SAEs, incidence of AEs and SAEs by organ systems, severity, and AEs' relationship to donepezil are calculated and/or assessed by calculating the number of patients having AEs and SAEs, the prevalence of AEs and SAEs and their 95% confidence intervals (95% CI). Laboratory abnormalities such as changes in alanine aminotransferase (ALT) and aspartate aminotransferase (AST), and changes in EKG and ECG such as HR, QT, QTc are summarized and described using means, standard deviation (SD), median, maximal, minimal, 25th and 75th percentile values, and further analyzed with paired *t*-test. Correlations of AEs and various risk factors are first assessed with univariate logistic regression analysis, and variables included patients' medical history (history of neurological, cardiovascular, mental, liver and gastrointestinal diseases), age (grouped into ≤ 75 and > 75 years), gender, body weight (≤ 55 kg and > 55 kg), APOE genotype ($\epsilon 2/\epsilon 2$, $\epsilon 3/\epsilon 3$, $\epsilon 4/\epsilon 4$, $\epsilon 2/\epsilon 3$, $\epsilon 2/\epsilon 4$, and $\epsilon 3/\epsilon 4$), the presence or absence of APOE $\epsilon 4/\epsilon 4$, concomitant medications (cardiovascular and cerebrovascular, gastrointestinal, liver, neurological, mental and hypoglycemic medications), and duration of donepezil 5mg/day treatment prior to the study (days). Forward stepwise multivariate logistic regression analysis is subsequently performed to

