further assess correlations between various risk factors and incidence of AEs using variables chosen from those used in the univariate analysis (SLSTAY=0.3, a significance value of 0.3 is required for a variable to stay in the multivariate model).

MMSE and ADCS-ADL are assessed at each visit. Their changes at each visit from baseline are calculated. Factors affecting MMSE and ADCS-ADL changes are assessed with a mixed model-repeated measures using an autoregressive covariance structure. Variables are the same as those used in the univariate analysis of correlations between AEs and various risk factors

All analyses are performed with SAS 9.4 (SAS Institute Inc.; Cary, NC, USA), data is analyzed with a two-tailed hypothesis, and a *p* value < 0.05 is considered to indicate statistical significance.

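### APOE genotyping is scheduled only at Visit 2, so safety-set patients who leave earlier have no planned genotype for the APOE–AE secondary endpoint

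*Protocol*

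**What the plan says.** In the protocol's PROCEDURES, the "APOE genotyping test" is item 4 under the heading "Visit 2 (maintain 10mg dose within 7 days after 4 weeks"). It is not listed at Visit 1 or Visit 3, and the laboratory panel in section 1.5 contains no genotype. Extra safety follow-ups are allowed at any time, but no sample is planned at them. No early-termination visit is described.

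Section 1.4 makes the APOE question a secondary endpoint (item 4): "Correlation analysis between Apo-E genotyping and adverse events of donepezil". Item 1 of the same list shows that some AE withdrawals are expected: "Monitor and record the number of patients withdrew from trial for adverse events".

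The SAP defines the safety set as "patients who receive at least one dose of donepezil 10mg/day and have at least one safety evaluation". Protocol section 1.3 sets the same two kinds of condition: at least one intake of drug and at least one safety evaluation. Reaching Visit 2 is not required in either place.

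The SAP enters APOE in the univariate logistic regressions of AEs, both as six genotypes and as "the presence or absence of APOE" ε4/ε4. The forward stepwise model then uses "variables chosen from those used in the univariate analysis". No rule is given for a missing genotype; LOCF is specified for main-variable and efficacy data only.

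**The concern.** The population for the AE analyses is fixed by one dose and one safety evaluation, but the exposure for secondary endpoint 4 is measured only in patients who reach a later milestone. Patients who leave for an AE before that milestone are all AE cases, so whether the genotype is known is tied to the outcome being analysed.

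The plan describes one such route. Under DRUG DOSAGE AND FORMULATION, a patient who fails a second attempt at 10 mg is counted as discontinued, possibly without ever having had 4 weeks on that dose.

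At stake are the completeness of the APOE–AE analysis and, under a specific condition set out below, the validity of its odds ratio. Genotype does not change with time or treatment, and the documents give no reason for waiting until Visit 2.

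**Working it through.** **Plan's own figure.** None is stated for the APOE–AE endpoint. The 461 evaluable patients are for the primary endpoint and reproduce: an exact 95% interval at 76% has total width 0.07996 at n = 461. The 554 to be enrolled is 461 × 1.2 = 553.2, rounded up. I use 554 below only as a head count.

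**Who is in the gap**

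| Patient | In safety set? | Planned genotype? |
|---|---|---|
| Takes 10 mg, has a safety evaluation, leaves before Visit 2 | Yes | No |
| Takes 10 mg, leaves with no safety evaluation | No | No, but not part of this analysis |
| Returns to 5 mg, re-escalates successfully | Yes | Yes, at a later Visit 2 |
| Reaches Visit 2 | Yes | Yes |

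Only the first row is affected.

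**When the odds ratio is biased.** Let p be the true AE risk in a genotype group and w the share of the whole group that leaves with an AE before Visit 2. Among genotyped patients the AE odds are (p − w)/(1 − p), so

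observed OR = true OR × [1 − w1/p1] / [1 − w0/p0].

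The governing quantity is w/p, the proportion of AE patients who leave early. If w/p is equal in the two groups, the bracketed terms cancel and there is no bias, however many AE cases are lost.

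**Numbers (all assumed; the documents give no early-exit rate, genotype frequency or genotype-specific risk).** Risks 82% vs 72%: true OR = (0.82/0.18)/(0.72/0.28) = 1.77.

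| w1 vs w0 | w1/p1 vs w0/p0 | Observed OR |
|---|---|---|
| 6% vs 3% | 7.3% vs 4.2% | (0.76/0.18)/(0.69/0.28) = 1.71 |
| 12% vs 5% | 14.6% vs 6.9% | (0.70/0.18)/(0.67/0.28) = 1.63 |
| 5% vs 12% | 6.1% vs 16.7% | (0.77/0.18)/(0.60/0.28) = 2.00 |
| 12% vs 10.5% | 14.6% vs 14.6% | (0.70/0.18)/(0.615/0.28) = 1.77 |
| 8% vs 8% | 9.8% vs 11.1% | (0.74/0.18)/(0.64/0.28) = 1.80 |

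The last two rows make the point. Unequal group-level loss with equal w/p leaves the OR alone. Equal group-level loss with slightly unequal w/p moves it a little. Bias can go either way.

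**Against sampling error.** Take the planned ε4/ε4 contrast, assume ε4/ε4 is 10% of 554 (55.4 vs 498.6 patients), and keep the overall AE rate at the planned 76%. With OR 1.77 the risks are 84.2% vs 75.1%. The variance of the log OR is the sum of reciprocal cell counts:

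1/46.6 + 1/8.75 + 1/374.4 + 1/124.2 = 0.146, so SE = 0.383.

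Most of it (1/8.75 = 0.114) comes from ε4/ε4 patients without an AE, who are not the ones lost. Two-sided 5% Wald power with complete genotyping is 32%.

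- 6% vs 3%: 55.4 × 0.06 + 498.6 × 0.03 = 18 patients lost; SE 0.385; bias 0.09 SE; power 29%.
- 12% vs 5%: 55.4 × 0.12 + 498.6 × 0.05 = 32 lost; SE 0.388; bias 0.22 SE; power 24%.

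**The case against.** A reader might infer that missingness tied to the outcome is enough to bias the result. It is not: loss that depends on AE status alone leaves an odds ratio unchanged. Bias needs early exit among AE patients to differ by genotype, and the documents give no indication that it does.

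A reader might also count every early dropout as lost to this endpoint. The safety set needs a safety evaluation as well as a dose. Neither document says whether that evaluation must follow dosing, and Visit 2 is the first scheduled evaluation on 10 mg. A patient who leaves before then with no contact may be outside the set whatever is done about genotyping.

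The plan limits early exit. Inclusion criterion 4 requires at least four weeks on 5 mg before screening, and the dosing section allows a return to 5 mg and a second attempt. A patient counted as discontinued is not said to be lost to follow-up or sampling. The text is a synopsis, so fuller procedures may provide for a withdrawal sample.

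Finally, for a rare contrast such as ε4/ε4, group size limits the analysis more than visit timing does.

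All of this stands, and it bounds the point. It does not remove it: in these documents a patient can be in the safety set, with an AE, and have no planned genotype.

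**Conclusion.** The gap is real and minor. Safety-set patients who leave before Visit 2 have no planned genotype in these documents and fall out of secondary endpoint 4 and of any multivariate AE model that includes APOE. The result is a loss of AE cases and some precision.

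Bias in the APOE odds ratio is conditional on the early-leaving proportion of AE patients differing by genotype. In the two main assumed cases the odds ratio falls from 1.77 to 1.71 or 1.63, which is 0.09 or 0.22 of a standard error for a 10% ε4/ε4 group. These sizes rest wholly on assumed risks, exit rates and genotype frequency, so a material bias is not shown. The primary endpoint does not use genotype and is unaffected, as are univariate AE analyses of the other risk factors.

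**What to change.** In the protocol, move the APOE sample from Visit 2 to Visit 1, using the blood already drawn there after consent. Assay it for every patient who takes at least one 10 mg dose; this covers the whole safety set. For patients already past Visit 1, sample at the next contact or at withdrawal. In the SAP, add a sentence reporting the number of safety-set patients without a genotype, by AE status.

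The cost is a one-line protocol amendment at all centres, a check that consent covers the earlier genetic sample, and assays for early leavers (18 or 32 in the two cases above). Because Visit 1 also serves to establish suitability, samples would be drawn from some patients who fail screening or never start 10 mg; the documents do not give that number. No extra visit is needed.
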